## Synopsis

Title	Dose-intensified Image-Guided Fractionated Stereotactic Body Radiation Therapy for Painful Spinal Metastases versus Conventional Radiation Therapy: a Randomised Controlled Trial (DOSIS RCT)
Short title	DOSIS RCT
Sponsor / Sponsor- Investigator	[name] [name]
Protocol version and date	Version 4.0; 11/12/2020
Trial registration	www.clinicaltrials.gov : NCT02800551 www.kofam.ch/de/studienportal : SNCTP000002145
Study category and rationale	
Type: Clinical trial.
 
Subtype and Category: Clinical trials with interventions that are neither a therapeutic product nor a transplant product, nor a transplant, Category A.
 
Rationale for the risk category: Radiation therapy of the spinal metastases is indicated for the trial population regardless of their participation in the trial. Stereotactic body radiation therapy (SBRT) is a currently used and established treatment for painful spinal metastases. The interventions under investigation therefore involve no more than minimal additional risks and stress for the participating patients.

Study background and rationale	
Radiation therapy is an effective palliative treatment for painful spinal metastases. Because metastatic disease is considered incurable and uncontrollable, palliation - pain relief, stability of the vertebra and stabilisation/improvement in neurological functions – is the primary treatment goal. Recent improvements in diagnosis, systemic and supportive treatments offer a chance to extend the life span of patients with spinal metastases beyond several months to several years. With longer survival, the patients are at higher risk of metastatic tumour recurrence, especially patients without purely osteoblastic spinal metastases, a factor associated with poor local metastasis control. Thus, there is a need for a treatment that would ensure both durable pain control and metastatic tumour control in the patients with longer life expectancy, ensuring long-term palliation.
 
With the introduction of high dose stereotactic radiosurgery (SRS) and stereotactic body radiation therapy (SBRT), radiation doses become “curative” as compared to “palliative” low doses of conventional radiation therapy. The treatment goal has shifted from short-term symptom control to long-term local metastasis control and makes SRS and SBRT a candidate treatment for painful spinal metastases. Despite its promising results, single-fraction SRS is associated with more recurrences in the epidural space and more frequent vertebral compression fracture (VCF). Hypofractionated SBRT may overcome limitations of single-fraction SRS by redefining the target volumes and improving metastatic disease control while minimising radiation-induced toxicity. We hypothesise that hypofractionated SBRT employing simultaneous integrated boost (SIB) allows radiation dose escalation in metastatic tumours with or without epidural involvement without

	
increasing the risk of radiation-induced myelopathy and VCF. Radiotherapy dose escalation is expected to achieve long-term local metastasis control and thereby long-term pain control and long-term palliation. Hence, a randomised clinical trial with pain response at six months (primary end-point) and metastatic tumour control (secondary endpoint) in patients with painful spinal metastases and a longer life expectancy was initiated. We expect the results of this trial to be practice changing.

Study type/design	
This is an international, multicentre, randomised, open-label, prospective, controlled study. This study additionally includes a prospective observational arm for patients not eligible for randomisation who are treated in analogy to arm A of the randomised arm.

Primary objective	
Randomised arm To compare long-term pain response after dose-intensified image-guided hypofractionated SBRT employing SIB versus conventional radiation therapy for painful spinal metastases.
 
Prospective observational arm To assess the long-term level of pain after dose-intensified image-guided hypofractionated SBRT employing SIB

Hypothesis	
Randomised arm Dose escalation for painful spinal metastases using image-guided hypofractionated SBRT provides superior long-term pain response without adding toxicity as compared to conventional radiation therapy.
 
Prospective observational arm To prospectively evaluate safety and efficacy of SBRT for vertebral metastases; no formal statistical endpoint will be tested.

End-points	
Randomised arm Primary end-point:
 
 
• Pain response - improvement by <math>\geq 2</math> points on the pain Visual Analogue Scale at 6 months post-treatment at the treatment site.
 
 
Secondary end-points:
 
 
• Local metastasis control;
 
• Overall survival;
 
• Cancer-specific survival;
 
• Quality of life (QoL);
 
• Acute and late toxicity.
 
 
Prospective observational arm Primary end-point:
 
 
• Pain response - improvement by <math>\geq 2</math> points on the pain Visual Analogue Scale at 6 months post-treatment at the treatment site.
 
 
Secondary end-points:
 
 
• Local metastasis control;
 
• Overall survival;
 
• Cancer-specific survival;
 
• Quality of life (QoL);
 

	
 
• Acute and late toxicity.
 
 
Both arms  Exploratory end-points:
 
 
• Time interval from patient presentation to start of SBRT;
 
• Central collection of all radiotherapy treatment plans for QA analyses.
 
• Central collection of all follow-up imaging for normal tissue response analyses of the vertebra on CT and MRI imaging to dose-intensified SBRT.
 

Treatment	
Both arms  Stratification by centre.
 
Randomised arm  Patients eligible for the randomised arm will be randomised in a 1:1 ratio to either of the following regimes:
 
Arm A (investigational) – investigational treatment  Image-guided hypofractionated SBRT using SIB to escalate radiation dose in the tumour (high-dose target volume) while maintaining a conventional dose in the un-involved segments of the affected vertebrae (conventional-dose target volume).
 
 
• in the case of no epidural involvement: 40 Gy and 20 Gy in 5 fractions to the high-dose and conventional-dose target volume, respectively;
 
• In the case of epidural involvement: 48.5 Gy and 30 Gy in 10 fractions to the high-dose and conventional-dose target volume, respectively;
 
 
or
 
Arm B (control) – standard treatment  External 3-dimensional conformal radiotherapy aiming at homogeneous irradiation of the affected vertebrae: each centre has to choose one fractionation protocol and use this one consistently within this study
 
 
• 20 Gy in 5 fractions
 
• 30 Gy in 10 fractions
 
 
Prospective observational arm  Patients eligible for the prospective observational arm (free of pain, purely osteoblastic metastases or refusal of randomisation), will be treated according to the investigational arm (arm A) of the randomised arm of the trial.

Number of patients	
Randomised arm  160 participants will be recruited to the study. Based on prior research, a 40% pain response rate (<math>\geq 2</math> point improvement based on VAS) is expected in the standard treatment group and a 30% difference in pain response is expected between groups. At least 80 patients are needed

	
in each treatment group to have 90% power of detecting this difference at the 5% level of significance in the presence of a 30% dropout rate.
 
Prospective observational arm The number of patients in the non-randomised part (observational arm) is not pre-defined because no formal statistical endpoint will be tested.

Inclusion criteria
	
Both arms Eligible patients have to provide written informed consent and must be able to understand and be willing to sign the written informed consent. Entry in the study is defined as the signing of the informed consent.
 
 
• Established histological diagnosis of a malignant primary or metastatic tumour;
 
• Histologically, radiologically or scintigraphically proven spinal metastasis;
 
• Age <math>\geq 18</math> years old;
 
• Karnofsky performance status <math>\geq 60\%</math>.
 
• Life expectancy <math>\geq 1</math> year according to investigator`s estimate
 
 
Randomised arm
 
 
• Osteolytic or mixed osteolytic/osteoblastic lesion
 
• Pain in the affected spinal region
 
• Willingness to undergo randomisation
 
•
 
 
Prospective observational arm
 
 
• Purely osteoblastic lesions or no pain in the affected spinal region or unwillingness to undergo randomisation
 


Exclusion criteria
	
Both arms
 
 
• “Radiosensitive” histology of the primary tumour, e.g., lymphoma, small-cell lung cancer, multiple myeloma, germ cell tumours;
 
• Progressive neurological symptoms/deficit;
 
• More than 3 (cervical spine) or more than 4 (thoracic, lumbar and sacral spine) continuously affected vertebrae in one target site;
 
• More than 2 treatment sites;
 
• Spinal Instability Neoplastic Score (SINS) 13 – 18 (unstable);
 
• Unable to tolerate treatment (unable to lie flat and immobilized);
 
• Previous radiotherapy of the region at the level of the affected vertebrae;
 
• Previous radionuclide therapy within 30 days before stereotactic body radiation therapy;
 
• Previous surgery (stabilisation) of the affected vertebrae;
 
• Patients with allergy to contrast agents used in computer tomography (CT) and magnetic resonance (MR) imaging or patients who cannot be premedicated to use contrast agent;
 
• Pregnant or lactating women;
 
• Women of child bearing potential or sexually active males not willing to use effective contraception while on treatment and 3 months after the end of treatment;
 

	
 
• Mental conditions rendering the patient unable to understand the nature, scope, and possible consequences of the study;
 
• Patients unlikely to comply with protocol, i.e. uncooperative attitude, inability to return for follow-up visits, and unlikely to complete the study.
 
 
Randomised arm
 
 
• Purely osteoblastic lesions;
 
• No pain in the affected spinal region
 
• Unwillingness to undergo randomisation
 
 
 
• Prospective observational arm
 
• See “both arms” (no additional exclusion criteria)
 


Study procedures
	
Both arms Informed Consent Prior to any study specific measures (including screening measures), patients must sign the informed consent form, after nature, scope, and possible consequences of the clinical study have been explained to them in a form understandable for them.
 
Both arms Screening All patients are screened for eligibility before treatment allocation. The following will be assessed:
 
 
• Review of eligibility criteria;
 
• Medical history;
 
• Physical and neurological examination;
 
• Height, weight, vital signs, Karnofsky performance status;
 
• Recording of all preexisting symptoms;
 
• Recording of pain and pain medications;
 
• Recording of concomitant medications;
 
• Radiology:             
 
○ CT scans;
 
○ MR scans;
 
○ Bone scans or positron-emission tomography scans;
 
 
 
• Pregnancy test for women of child bearing potential;
 
• Decision of a study centre tumour board on radiation therapy for painful spinal metastases;
 
• Health-related QoL as measured by the EORTC QLQ-C15-PAL, EORTC-BM22 and EQ-5D-5L patient reported questionnaires;
 
• Willingness to undergo randomisation
 
 
Randomised arms Treatment phase Patients will be treated according to arm A (investigational treatment) or arm B (standard treatment).
 
In arm A, patients immobilized in treatment position will undergo planning CT and MR. Two planning target volumes (PTVs) will be determined on CT and MR as follows: 1) the high-dose gross tumour

	
volume defined on CT/MR that is isotropically expanded with a 2 mm margin (the high-dose PTV) excluding the planning-at-risk volume (PRV) of the spinal cord and 2) the entire affected vertebra expanded isotropically with a 2 mm margin minus the high-dose PTV (the conventional-dose PTV or standard PTV, respectively). The spinal cord will be included into the conventional-dose PTV. In Arm A (investigational treatment) patients will receive image-guided static or rotational intensity-modulated radiation therapy with a prescription dose of 40 Gy and 20 Gy in 5 fractions to the high-dose PTV and conventional PTV, respectively, in the case of no epidural involvement; 48.5 Gy and 30 Gy in 10 fractions, if there is epidural involvement. There will be daily image-guided online correction of patient position errors.
 
In Arm B, patients will receive 3-dimensional conformal radiation therapy of the involved vertebrae using an institutional image-guidance protocol with a median prescription dose of 20 Gy in 5 fractions or 30 Gy in 10 fractions, depending on institutional protocol.
 
For arm A and arm B, the following procedures will be completed weekly during treatment:
 

• Physical and neurological examination;

• Weight, vital signs, Karnofsky performance status;

• Assessment of pre-specified protocol-specific adverse events;

• Recording of all other adverse events;

• Recording of pain and pain medications;

• Health-related QoL as measured by the EORTC QLQ-C15-PAL, EORTC-BM22 and EQ-5D-5L patient reported questionnaires (once at the last day of treatment).

 
There will be a prospective collection of planning CT and MR scans, treatment plans and all follow-up images of all patients enrolled into the study.
 
Prospective observational arm
 
Treatment phase
 
In the Prospective observational arm, patients will be treated exactly as patients in arm A of the randomised arm and they will undergo the same procedures.
 
Both arms
 
Post-treatment phase
 
For all patients, the following will be completed within 1 month <math>\pm</math>1 week (first follow-up visit):
 

• Physical and neurological examination;

• Weight, vital signs, Karnofsky performance status;

• Assessment of pre-specified protocol-specific adverse events;

• Recording of all other adverse events;

• Recording of pain and pain medications;

• Recording of concomitant medications;

--	--

	
 
Health-related QoL as measured by the EORTC QLQ-C15-PAL, EORTC-BM22 and EQ-5D-5L patient reported questionnaires.
 
 
Both arms
 
Follow-up visits
 
Patients will be followed-up for 2 years after treatment completion or until death. Follow-up visits are scheduled at 3, 6, 12 and 24 months (<math>\pm 4</math> weeks) after treatment. The following procedures will be done at every follow-up visit:
 
 
Physical and neurological examination;
 
Weight, vital signs, Karnofsky performance status;
 
Assessment of pre-specified protocol-specific adverse events;
 
Recording of all other adverse events;
 
Recording of pain and pain medications;
 
Recording of concomitant medications;
 
Radiology as clinically indicated for osteolytic lesions, based on institutional protocol: CT and/or MR scans;
 
Health-related QoL as measured by the EORTC QLQ-C15-PAL, EORTC-BM22 and EQ-5D-5L patient reported questionnaires.
 

Study schedule	First quarter Q1 2016 (first patient enrolment) – Q4 2023 (last patient enrolment)
Sponsor-Investigator and Coordinating-Investigator	
[name] [name]          Department of Radiation Oncology          University Hospital Zurich          [name]          [name]          Switzerland          [contact]          [contact]          e-mail: [contact]

Study centres	Currently participating centres: 20 sites in Switzerland and in Europe
Statistics	
Randomised arm
 
Sample size
 
160 participants will be recruited to the study. Based on prior research, a 40% pain response rate (<math>\geq 2</math> point improvement based on VAS) is expected in the standard treatment group and a 30% difference in pain response is expected between groups. At least 80 patients are needed in each treatment group to have 90% power of detecting this difference at the 5% level of significance in the presence of a 30% dropout rate.
 
Statistical analysis
 
Statistical analysis will be done in three populations: 1) Intent-to-Treat population (ITT) including all patients who were randomised and received at least one fraction of radiation therapy; 2) Per Protocol population (PP) including all patients of the ITT who have received study treatment according to randomisation without significant protocol violations and 3) safety-analysis set including all patients who were randomised and received at least one fraction of radiation therapy. To compare long-term pain control, Pearson's chi-square test with a continuity correction will be used on pain response rates across the two

	
treatment arms. Wilson-method 95% confidence intervals will be provided for the pain response rate in each treatment group. The risk difference and its confidence interval will be provided as an effect measure, easily allowing for readers to calculate the 'number needed to treat'. Additionally, the odds ratio will be provided as a second effect measure. This measure allows for easy extension to logistic regression if other characteristics vary greatly across treatment groups. If daily oral morphine equivalent or epidural involvement vary greatly across treatment groups, a logistic regression model including treatment, daily oral morphine equivalent, epidural involvement, and centre will be used, which yields an odds ratio and its 95% confidence interval to summarize the difference in pain response between the treatment groups while controlling for other factors.
 
The Kaplan Meier estimator will be used for overall survival across the two treatment groups. (Semi-) Competing risk methods will be used to address the following events: local metastasis recurrence, cancer-specific death, and death by other causes. Cumulative incidence functions and sub-distribution hazards accounting for competing risks will be computed.
 
All safety analyses will be conducted on the safety-analysis set according to treatment received. For pre-specified protocol specific AEs, the point estimate of the difference between treatment arms, with 2-sided 95% CIs, will be provided. All other safety analyses will be presented in tabular format with the appropriate summary statistics for each treatment arm. QoL descriptive analysis will include the subset of the PP patients.
 
Prospective observational arm
 
Sample size
 
The sample size will not be pre-defined since no formal statistical hypothesis will be tested. For the University Hospital Zurich, we assume ca. 40 patients.
 
Statistical analysis
 
The statistical analysis will be mainly descriptive and exploratory. We report mean and standard deviation for continuous variables and median and interquartile range for ordinal variables and number and percentage for categorical variables. For the primary outcome, the proportion of patients with clinically relevant pain reduction will be estimated with Wilson 95% confidence intervals. Kaplan Meier curves will be plotted for overall survival. Competing risk methods will be used for local metastasis control, cancer-specific survival, and overall survival. Descriptive statistics will be used to describe quality of life outcomes and safety outcomes.
 
Interim Analysis
 
If the trial fails to recruit at least 50% of the initially planned patients in the randomised arms until 12/2020 (originally planned recruitment end), an interim safety and efficacy analysis of both randomised and prospective observational arms will be conducted.
 
If no safety concerns are raised after this interim analysis and there is a clinically relevant benefit of at least 10% for the experimental regimen

--	---

Dose-intensified Image-guided Fractionated Stereotactic Body Radiation Therapy for Painful Spinal Metastases versus Conventional Radiation Therapy: a Randomised Controlled Trial (DOSIS RCT)

	regarding the primary endpoint, the recruitment will be continued. Otherwise, the study will be terminated due to slow accrual and futility.
GCP statement	This study will be conducted in compliance with the protocol, the current version of the Declaration of Helsinki, the ICH-GCP or ISO EN 14155 (as far as applicable) as well as all national legal and regulatory requirements.

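### The observational arm's primary end-point needs a fall of at least 2 VAS points, yet the arm admits pain-free patients, who can never respond and stay in the denominator

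*Protocol*

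**What the plan says.** All references are to the Protocol, Synopsis.

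- **Primary objective (observational arm):** "To assess the long-term level of pain after dose-intensified image-guided hypofractionated SBRT employing SIB".
- **End-points:** the primary end-point has the same wording for the randomised and the observational arm, an improvement of at least 2 "points on the pain Visual Analogue Scale at 6 months post-treatment at the treatment site". It carries no baseline condition and no alternative rule for patients who start without pain.
- **Treatment:** patients are described as "eligible for the prospective observational arm (free of pain, purely osteoblastic metastases or refusal of randomisation".
- **Inclusion criteria (observational arm):** "Purely osteoblastic lesions or no pain in the affected spinal region or unwillingness to undergo randomisation". The three conditions are joined by *or*, so absence of pain is sufficient by itself.
- **Exclusion criteria (observational arm):** the criteria common to both arms apply, with "no additional exclusion criteria".
- **Statistics (observational arm):** for the primary outcome, "the proportion of patients with clinically relevant pain reduction will be estimated with Wilson 95% confidence intervals". The arm's size is not fixed in advance: "For the University Hospital Zurich, we assume ca. 40 patients".

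**The concern.** Population, end-point and analysis are each clear, but they do not fit together. One of the three named routes into the arm is having no pain, and success is defined as losing at least 2 points of pain. For a patient at VAS 0 the best possible result is to remain at 0, and the plan scores that as failure.

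What is at stake is the meaning of the arm's main result. The arm is meant to describe how well SBRT works outside the randomised comparison, with the same treatment as arm A. If the response rate moves with the number of pain-free patients enrolled, it says little about the treatment. A reader who sets it beside the arm A rate, or beside the 40% expected under standard treatment, would be comparing different things.

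**Working it through.** **The plan's own figures.** The Synopsis gives no expected response rate or precision target for the observational arm, so there is nothing to reproduce there. The sample size of the randomised arm does reproduce. For 40% against 70%, two-sided 5% and 90% power without continuity correction, n = [1.960·√(2·0.55·0.45) + 1.282·√(0.40·0.60 + 0.70·0.30)]² / 0.30² = 55.7, rounded up to 56. Then 56/0.70 = 80 per group. This point does not touch that figure.

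**Inputs**

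| Input | Value | Source |
|---|---|---|
| Response | fall of at least 2 VAS points at 6 months | End-points |
| Pain-free patients admitted | yes, sufficient by itself | Treatment; Inclusion criteria |
| Pain-free patients later removed | no | Exclusion criteria; Statistics |
| Share *f* of patients with baseline below 2 | not given | assumed: 10%, one third, one half |
| Response *r* among patients able to respond | not given for this arm | assumed 70%, i.e. the planning values 40% + 30 points |
| Illustrative size | 40 | Statistics (Zurich only) |

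**Step 1: who can respond.** A fall of 2 points requires a baseline of at least 2. Below that the probability of response is zero, whatever the treatment does.

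**Step 2: the reported rate.** With all patients in the denominator, R = r × (1 − f). Since r cannot exceed 1, R cannot exceed 1 − f.

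| f | Ceiling 1 − f | R at r = 70% |
|---|---|---|
| 0 | 100% | 70% |
| 10% | 90% | 0.70 × 0.90 = 63% |
| one third | 67% | 0.70 × 2/3 = 47% |
| one half | 50% | 0.70 × 0.50 = 35% |

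**Step 3: when case mix alone takes R below 40%.** Setting 0.70 × (1 − f) = 0.40 gives f = 1 − 0.40/0.70 = 43%. With a larger share than this, a treatment that works in 70% of patients with pain would show a rate below the planning value for standard treatment.

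**Step 4: what the Wilson interval would show.** The interval is [p + z²/(2n) ± z·√(p(1 − p)/n + z²/(4n²))] / (1 + z²/n), with z = 1.96. For 40 patients:

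| Pain-free | All patients | Patients able to respond |
|---|---|---|
| 10 of 40 | 21/40 = 52.5% (37% to 67%) | 21/30 = 70% (52% to 83%) |
| 20 of 40 | 14/40 = 35% (22% to 50%) | 14/20 = 70% (48% to 85%) |

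In the second row the all-patient interval excludes the 70% that holds among patients with pain. Enrolling more patients with the same mix would only narrow the interval around the wrong quantity.

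**Step 5: objective against end-point.** The objective asks for the level of pain. A patient who starts and ends at VAS 0 and one who starts and ends at VAS 8 are both non-responders. The end-point therefore cannot separate the best level from a poor one.

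**The case against.** **The arm is descriptive.** No hypothesis is tested, the size is open, and no formal comparison with arm A is planned. That is correct, so type I error is not at issue. But this is still the arm's primary end-point, the arm is said to evaluate efficacy, and a descriptive rate should describe something interpretable.

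**The distortion may be small.** Patients with pain also enter, by refusing randomisation or through osteoblastic lesions. At 10% pain-free, 70% becomes only 63%. This stands: the size is unknown. The direction is not, because any non-zero share lowers the rate.

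**The analysis plan may restrict the denominator, and the data allow it.** Pain is recorded at screening and at each follow-up visit, and general descriptive summaries are foreseen, so the level of pain can still be described. The statistical analysis plan was not available for this review. No information is lost, which makes the repair easy. The Protocol itself, however, fixes eligibility, end-point and primary analysis in a combination that does not work.

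**A stronger reading for the randomised arm.** The entry criterion there is "Pain in the affected spinal region", without a minimum score. A reader might infer that the randomised response rates are wrong too, or that the trial is underpowered for this reason. The Protocol does not support that. Patients without pain are excluded from randomisation, and only baselines above 0 and below 2 are affected, in unknown number. Randomisation balances such patients in expectation, so the comparison stays valid. The 40% is stated as the rate expected in the standard treatment group and may already reflect the enrolled mix. A new minimum score at entry would also leave a willing patient with an osteolytic lesion and a VAS of 1 eligible for neither arm, and would change the population of a trial whose Synopsis already provides for slow accrual.

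**A stronger reading for the interim analysis.** The possible interim safety and efficacy analysis covers the observational arm as well. A reader might infer that its rate decides whether recruitment continues. The Synopsis does not say so.

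**Conclusion.** The fault holds for the observational arm and follows from the Protocol's text without any outside figure. As written, the primary response rate includes patients for whom response is impossible, is capped at one minus their share, and does not match the arm's stated objective. Under the assumed 70% response among patients with pain, it would read 63%, 47% or 35% when 10%, one third or one half start pain-free. Both the 70% and the shares are assumptions. The ceiling is not.

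The harm is a misleading description and a rate that cannot be placed beside arm A. The randomised comparison and its sample size are unaffected by this point.

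**What to change.** In the Statistics and End-points text for the observational arm:

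1. Estimate the response proportion, with its Wilson interval, only in patients whose recorded baseline VAS at the treated site is at least 2.
2. For patients with a baseline below 2, report separately the VAS level at 6 months and the proportion without a rise of 2 points or more.
3. State the number of patients in each group and do not pool them into one rate.

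No change to the randomised arm's eligibility is needed for this point.

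The cost is wording plus a smaller denominator. In the example with half of 40 patients pain-free, the interval widens from about 28 points (22% to 50%) to about 37 points (48% to 85%), but it then refers to patients who can respond. The pain scores needed are already collected.

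### The set labelled 'Intent-to-Treat' omits randomised patients who never start radiotherapy, so no analysis set holds everyone randomised and the primary comparison can be biased in either direction

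*Protocol*

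**What the plan says.** The relevant text is in the protocol's Synopsis, Statistics, Randomised arm, Statistical analysis. It opens with "Statistical analysis will be done in three populations" and then defines them:

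- ITT: "Intent-to-Treat population (ITT) including all patients who were randomised and received at least one fraction of radiation therapy".
- Per protocol: "including all patients of the ITT who have received study treatment according to randomisation without significant protocol violations".
- Safety: "safety-analysis set including all patients who were randomised and received at least one fraction of radiation therapy".

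The ITT and safety conditions are identical. What separates the two is the grouping of patients: "All safety analyses will be conducted on the safety-analysis set according to treatment received". The text names no further set for the primary endpoint.

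Under Study type/design, the Synopsis describes an "international, multicentre, randomised, open-label, prospective, controlled study". The primary endpoint is pain response 6 months after treatment, and the follow-up visits are likewise timed from treatment.

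**The concern.** Receiving a first fraction happens after randomisation. A patient who is randomised but starts no radiotherapy falls outside the ITT set, therefore outside the per-protocol set, and outside the safety set as well. No planned analysis would show that such patients exist or how they differ by arm.

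If non-starting were unrelated to allocation and prognosis, little would be lost. Two features of this trial mean that cannot be taken for granted. Both patient and physician know the allocation, so a patient may withdraw on learning it. The route to the first fraction may also differ: for arm A the Synopsis states that "patients immobilized in treatment position will undergo planning CT and MR" and describes a plan with two target volumes, while arm B receives 3-dimensional conformal treatment under institutional practice. Patients may enter with a Karnofsky status as low as 60%, so deterioration before treatment is plausible.

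At stake is the protection that randomisation gives to the primary comparison. The label adds to the problem, because a reader of the results will take 'intent-to-treat' to mean that everyone randomised was analysed.

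**Working it through.** **Set membership.** Write R for randomised and F for at least one fraction of radiotherapy.

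- ITT = R and F.
- Per protocol = R and F, treated as randomised, without significant violations.
- Safety = R and F, grouped by treatment received.

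A patient with R but not F is in none of the three. The condition asks for radiotherapy, not the allocated radiotherapy, so a patient who crosses over and starts stays in. Only those who start nothing are lost.

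**The plan's own figure.** Inputs from the Synopsis: 40% v 70% response (40% plus a 30% difference), 5% level, 90% power, 30% dropout. With a two-sided test and no continuity correction:

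n = [1.960 × √(2 × 0.55 × 0.45) + 1.282 × √(0.40 × 0.60 + 0.70 × 0.30)]² / 0.30² = 55.7, so 56 per arm; 56 / 0.70 = 80 per arm.

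The stated 80 per arm reproduces, and nothing below changes it.

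**Size of the possible bias.** The protocol gives no non-starter rates, so xA and xB are assumed. Let those who start respond at 70% (arm A) and 40% (arm B), and count non-starters as non-responders.

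- Difference among starters: 0.70 − 0.40 = 30 points.
- Difference among all randomised: 0.70(1 − xA) − 0.40(1 − xB).
- Overstatement by the starters-only analysis: 0.70 xA − 0.40 xB.

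| xA | xB | All randomised, A | All randomised, B | Difference (points) | Overstatement (points) |
|---|---|---|---|---|---|
| 5% | 0% | 66.5% | 40.0% | 26.5 | +3.5 |
| 10% | 2% | 63.0% | 39.2% | 23.8 | +6.2 |
| 0% | 5% | 70.0% | 38.0% | 32.0 | −2.0 |
| 2% | 10% | 68.6% | 36.0% | 32.6 | −2.6 |
| 2% | 2% | 68.6% | 39.2% | 29.4 | +0.6 |
| 2% | 0% | 68.6% | 40.0% | 28.6 | +1.4 |
| 0% | 2% | 70.0% | 39.2% | 30.8 | −0.8 |

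At around 2% non-starting the shift is about 1 point. Its sign depends on which arm loses more patients.

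**A check under no true effect.** Suppose 40% of all randomised patients respond in each arm, and only arm B has non-starters (fraction f), who would have responded with probability q. The arm B rate among starters is (0.40 − f q) / (1 − f).

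- f = 5%: 42.1% if q = 0 and 36.8% if q = 1, so the A − B difference is −2.1 to +3.2 points.
- f = 10%: 44.4% to 33.3%, so −4.4 to +6.7 points.
- f = 2%: −0.8 to +1.2 points.

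With 80 per arm randomised, no other loss and an uncorrected normal approximation, the nominal 5% test at those extremes rejects about 5.8% to 6.9% of the time at f = 5% and 8.6% to 13.5% at f = 10%. These are limiting cases, not forecasts.

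**The case against.** The strongest reply is that the harm is hypothetical. The Synopsis notes that radiotherapy is indicated for these patients whether or not they join the trial, so few may never start, and crossovers who start are retained. Nor are the pre-treatment steps clearly separated by arm: the Synopsis also plans to collect planning CT and MR scans and treatment plans for all enrolled patients. This stands as a limit on size. It does not rescue the definition, which excludes on a post-randomisation event under an intention-to-treat label. Nor can this be left to a statistical analysis plan, because the protocol itself fixes the rule.

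A second reply is that redefining the set does not by itself supply data. With endpoint and visits timed from treatment, a patient who is never treated has no 6-month assessment. Counting only deaths as non-response would still leave living non-starters out of the primary comparison. This is correct, and the fix has to deal with it.

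Three stronger readings are tempting, and the documents do not support them.

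- *The definition inflates the SBRT effect.* It may, but the same formula gives understatement when arm B loses more patients, and no rates are given.
- *Power is really 78%, or 73% with the continuity correction.* Those figures follow if all 30% dropouts are kept as non-responders (0.70 × 0.70 = 49% v 0.40 × 0.70 = 28%, 80 per arm). They come from the handling of missing 6-month scores, not from the one-fraction rule, since a patient can start treatment and still have no score. The protocol says only "in the presence of a 30% dropout rate"; it does not say that dropouts include deaths, and inflating 56 to 80 is ordinary practice.
- *The ITT and safety analyses are the same.* Their membership is; their grouping need not be.

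**Conclusion.** The point holds. The population called ITT is a treated population, and none of the three sets contains all randomised patients. In an open-label trial this can bias the primary comparison, but neither direction nor size can be established from the protocol. Over assumed non-starter rates of 0% to 10%, with the planned response rates among starters and non-starters counted as non-responders, the worked cases run from an overstatement of 6.2 points to an understatement of 2.6 points, against a planned difference of 30. If non-starting is rare and balanced the effect is negligible: 0.6 of a point at 2% in each arm. The case for change rests on the wrong definition and the low cost of correcting it, not on evidence that non-starting is common.

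**What to change.** - Define ITT as all randomised patients, analysed in the arm to which they were allocated, and name it as the set for the primary analysis.
- Keep the one-fraction condition for the safety set. If the present ITT definition is still wanted, retain it as a sensitivity analysis labelled 'modified ITT'.
- State how patients who never start radiotherapy are counted at 6 months: for example as non-responders, or by a pain score at an assessment timed from randomisation. Without such a rule they have no endpoint and drop out again.

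**Cost.** The redefinition is wording. The counting rule is a further decision, and the second option also means following patients who never start. The estimate may become slightly less favourable. The sample size is not threatened by this change alone: with 80 per arm, no other loss and 5% non-starters in each arm kept as non-responders (66.5% v 38.0%), the uncorrected formula gives 95.7% power, against 97.4% with no non-starters.
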